## 12.10 QUANTITATIVE ELECTROENCEPHALOGRAM (qEEG) MONITORING AND REPORTING

Scalp-recorded EEG will be collected on all Subjects in the SAD study for approximately 1 hour immediately preinfusion, for 1 hour after the start of the infusion and for a subsequent hour following a 1 hour break (ie, collecting EEG data during hours  $2\rightarrow3$  after the start of the infusion; total of 3 hours recording after the start of dosing). During this time, there will be three, 10-minute intervals specifically dedicated to collecting 'clean' resting-state (5 minutes) and visual-evoked-potential (5 minutes). The remainder of the session will entail passive recording of the EEG during other study activities.

High-definition EEG will be acquired through a 64-channel Brain Products actiCHamp systems using active electrodes positioned according to an equidistant spacing, covering the whole head from slightly above the eyebrows to below the inion. The EEG leads will include horizontal and vertical electrooculography, which will be used to identify and remove periods of ocular artifact during postprocessing of the data. The EEG leads will be placed in a nylon fabric EasyCap. Prior to recording data, a thorough impedance check of the electrodes will be done to ensure high-quality recording. During the drug infusion, subjects will remain in a recumbent position with their head slightly raised. Approximately 40 minutes prior to infusion, as well as at approximately 40 and 160 minutes after the start of the infusion, participants will perform 10 minutes of dedicated EEG activities. To begin, the subject will be cued to undergo a 5-minute routine in which they stay comfortably in a recumbent position with their eyes closed and relax. This interval will allow for capture of "clean intervals" from which to derive time-frequency, and spectral power measures. Immediately following this, subjects will perform a brief, 5-minute visual evoked potential paradigm in which they passively view a contrastreversing checkerboard stimulus alternating pseudo-randomly at approximately 0.5 Hz.

Subjects will spend the bulk of the remainder of the EEG recording time in a recumbent position. In the event subjects must leave the bed, the recording file will be paused, the EEG head cap will remain on the participant's head while cables that connect to the amplifier will be ejected and clipped to the participant's shirt to allow free movement. Once the participant returns, the cables will be inserted back into the amplifier, a brief impedance check will be done to ensure high-quality recording, and recording will then continue. Additional details of the EEG are in the MOP.

The National Institutes of Health Experimental Therapeutics and Pathophysiology Branch will receive the collected data. The data will undergo epoch-by-epoch visual artifact correction/rejection. Quantitative EEG analysis will only be carried out if a minimum of 30 seconds of waking, artifact free data are available for any resting-state scan. The data will undergo Laplacian transformation to produce current density estimates. The current density data will undergo spectral analysis via Fast Fourier Transform (FFT) with boxcar windowing to generate power estimates in the following frequency bands: delta (2-7Hz), theta (7-9Hz), alpha (9-12Hz), beta (12-30Hz), and gamma (30-60Hz). This will be carried out with the LORETA software. At each voxel (n=2394; voxel resolution=7 mm3), current density will be computed as the squared magnitude of the intracerebral current density within each of the 5 frequency bands (unit: amperes per square meter,  $A/m^2$ ). Current density estimates will be intensity-normalized to unity and log-transformed before statistical analyses. This will be carried out in 2second segments and averaged over the available artifact-free, waking data. These data will be used to estimate resting-state EEG current density. The primary qEEG outcome will be EEG gamma current density. Resting state EEG current density estimates in other frequency bands will be analyzed to evaluate the specificity of possible findings. Exploratory analysis for patterns of EEG activity that are predictors and correlates of outcome will be carried out using EEG power in all bands derived from all the electrodes, employing principal components analysis.

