# 13.3 qEEG DATA

Quantitative EEG (qEEG) data will be obtained for all study subjects in the SAD cohorts. This data will be collected over approximately 3 hours with predefined resting-state and visual evoked potential intervals. Analysis of the EEG data will include preliminary artifact correction using PCA-based techniques to identify biological artifacts that are not attributed to cortical activity. This will include scrutiny of the component spectral and spatial profiles, ultimately eliminating components that present with nontypical cortical activity. The qEEG parameters that will be studied include the ones discussed below. Other qEEG parameters may be evaluated postacquisition and will be described in the Statistical Analysis Plan.

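### The primary qEEG outcome, gamma over 30-60 Hz from an untapered FFT on 2-second segments, is open to leakage from alpha and slow drift and, depending on an unstated band edge, to 60 Hz mains

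*Protocol*

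**What the plan says.** Protocol 12.10 sets out the resting-state method. Subjects "stay comfortably in a recumbent position with their eyes closed and relax" for 5 minutes, at about 40 minutes before infusion and about 40 and 160 minutes after its start. After a Laplacian transformation the current density data undergo "spectral analysis via Fast Fourier Transform (FFT) with boxcar windowing to generate power estimates in the following frequency bands". The top two bands are "beta (12-30Hz), and gamma (30-60Hz"), and alpha is 9-12 Hz. On segmentation: "This will be carried out in 2second segments and averaged over the available artifact-free, waking data". A scan is analysed if "a minimum of 30 seconds of waking, artifact free data are available for any resting-state scan". Estimates are normalised to unity and log-transformed. On the endpoint: "The primary qEEG outcome will be EEG gamma current density". The other bands are analysed to judge how specific a gamma finding is.

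Three cleaning steps are named:
- removal of ocular artifact using electrooculography leads (12.10);
- visual review: "The data will undergo epoch-by-epoch visual artifact correction/rejection" (12.10);
- "preliminary artifact correction using PCA-based techniques to identify biological artifacts that are not attributed to cortical activity" (13.3).

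The relative-power analysis in 13.3 applies an FFT to the raw EEG and states no window. Further EEG detail is deferred to the Manual of Procedures (MOP), and the analysis to a separate qEEG plan. Neither was available for this review. qEEG is an exploratory objective in Protocol section 3.0 and a secondary one in SAP 4.2.

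**The concern.** The boxcar is a stated choice, not a gap in the text. Its side lobes decay slowly, so strong low-frequency power in a short segment reappears at high frequencies. Alpha is typically prominent with the eyes closed, and gamma is typically small, so a tiny fraction of alpha can matter. Averaging over segments does not help, because leakage adds to the expected power in every segment.

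The band also ends exactly at 60 Hz, which is taken here as the mains frequency because the single site is in the US. Visual review and a PCA aimed at biological artifacts are not directed at a steady line.

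Two consequences follow. Contamination that stays constant dilutes a true log-scale gamma effect. Contamination that moves with alpha can produce a gamma change that is not there, and it weakens the other-band specificity check, since alpha and gamma are no longer measured separately.

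**Working it through.** The documents give no expected gamma, alpha, drift or mains amplitude and no qEEG power calculation, so there is no stated figure to reproduce. Amplitudes below are assumptions shown as ranges, in scalp-voltage terms.

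**Bins.** Segment length T = 2 s gives a bin width of 1/2 = 0.5 Hz. The 30-60 Hz band spans bins k = 60 to 120, and 60 Hz falls exactly on bin 120. The 30-second minimum is 15 segments; 5 minutes is 150.

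**Alpha leakage fraction.** A unit-power tone at frequency f, averaged over phase, puts sin²(π(fT − k)) / (π²(fT − k)²) into bin k, plus the same expression with fT + k. Averaging sin² to 1/2 at mid-alpha (10.5 Hz, fT = 21) and summing over k = 60 to 120:
- direct term: Σ 1/(k − 21)² / (2π²) = 0.00081
- image term: Σ 1/(k + 21)² / (2π²) = 0.00027
- total: 0.00108, about 0.11%.

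Direct computation averaged over 9-12 Hz gives 0.11% (0.22% for a tone midway between bins). With a Hann taper it is about 8 × 10⁻¹¹.

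**Inflation of gamma** = 0.0011 × alpha power / gamma power.

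| Alpha rms | Gamma rms | Power ratio | Formula | Simulated (9-11 Hz alpha) |
|---|---|---|---|---|
| 10 uV | 2 uV | 25 | 2.8% | about 3% |
| 10 uV | 1 uV | 100 | 11% | about 10% |
| 20 uV | 2 uV | 100 | 11% | about 10% |
| 20 uV | 1 uV | 400 | 44% | about 42% |

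**False gamma change if alpha power halves and gamma does not change** = (1 + 0.00055R)/(1 + 0.0011R) − 1, where R is the alpha-to-gamma power ratio:
- R = 10: −0.5%
- R = 30: −1.6%
- R = 100: −5.0%
- R = 300: −12.4%
- R = 400, the extreme row of the table: 1.22/1.44 − 1 = −15%.

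**Drift.** A linear ramp of D uV across a segment adds D² × Σ 1/k² / (2π²), about 0.00043 D² uV². For D = 10, 20 and 50 uV this gives 0.04, 0.17 and 1.08 uV². Direct computation gives 0.04, 0.18 and 1.10, which is 4%, 18% and 110% of a gamma power of 1 uV². Simulated slow drift (0.05-0.5 Hz) of 30 uV rms adds about 0.8 to 1 uV². With a Hann taper, the 50 uV ramp contributes about 2 × 10⁻⁸ uV².

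**Mains, boxcar.**
- 60 Hz bin counted: 98-100% of a 59.95-60.05 Hz line enters gamma. Residual mains of 0.5 uV rms is 0.25 uV², so it adds 25% at gamma 1 uV rms and 0.25/4 = 6% at 2 uV.
- 60 Hz bin not counted: none of an exact 60 Hz line enters, about 0.25% of it at 60.02 Hz, and 1.4-1.8% at 60.05 or 59.95 Hz. The same 0.5 uV then adds at most 0.25 × 0.018 = 0.0045 uV², under 0.5% at gamma 1 uV.

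**Mains, Hann.** A taper alone does not solve this. About 83% of an exact 60 Hz line stays in 30-60 Hz if the bin is kept, and about 17% even if it is dropped, because the main lobe is wider. With the upper edge at 55 Hz, at most about 2 × 10⁻⁸ of the line enters.

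**Dilution.** With constant 25% contamination, a true +30% in gamma reads (1.30 + 0.25)/1.25 − 1 = +24%.

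**The case against.** A reader might infer that gamma as defined does include the mains line, that the 7, 9, 12 and 30 Hz bins are counted in two bands, and that the primary qEEG outcome is therefore misstated. The documents do not support this. Section 12.10 never says that band edges are inclusive; shared edges are common shorthand. With the 60 Hz bin left out, mains is negligible under the boxcar.

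Further points on the other side:
- **Unseen documents.** The MOP and qEEG plan may specify filtering or detrending. For mains and drift, the protocol shows an omission, not a demonstrated error. This does not answer alpha leakage: line or drift filtering leaves it in place, and the boxcar is expressly specified.
- **Pipeline.** The microvolt figures are for a single scalp signal. The outcome is Laplacian-transformed, LORETA-derived, normalised and logged, so the percentages are indicative only. This stands.
- **Drift.** Visual review may remove grossly drifting epochs, so the larger drift figures are upper-end cases. This stands.
- **Alpha change.** The −0.5% to −12.4% range is for halved alpha power. Halving amplitude is a fourfold fall in power and gives larger figures (at R = 400, 1.11/1.44 − 1 = −23%). The two should not be confused.
- **Bias.** Constant contamination dilutes an effect but creates none. Preinfusion recordings and 12 planned SAD placebo subjects help, and a large alpha effect would show in the alpha band as a warning. That warning would not say how much of the gamma change is leakage.
- **Importance.** No safety, PK or escalation conclusion rests on gamma in these documents, and stored recordings can be reprocessed. This limits the consequence.

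**Conclusion.** The concern holds as exposure to contamination, not as proof that gamma is misstated. The protocol chooses a boxcar FFT on short eyes-closed segments for a gamma outcome and names no taper, detrending or line-noise step. Leakage of about 0.1% of alpha power follows from that choice alone.

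Its effect runs from about 3% to 42% inflation over the assumed amplitudes (alpha 10-20 uV rms, gamma 1-2 uV rms), and a false change of about 1-12% if alpha power halves, at power ratios of about 10-300. Both rest on scalp-voltage assumptions not carried through LORETA. Drift adds to this only if it survives cleaning. Mains matters only if it survives acquisition and cleaning and the 60 Hz bin is counted. The change is worth making because gamma is the named primary qEEG outcome and the correction is cheap, but it bears on an exploratory objective (secondary in the SAP).

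**What to change.** In Protocol 12.10 and the qEEG analysis plan, before unblinding:

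1. Replace the boxcar with a Hann taper on 2-second segments with 50% overlap, after linear detrending.
2. Define gamma as 30-55 Hz.
3. Use half-open bands: 2 to <7, 7 to <9, 9 to <12, 12 to <30, and 30-55 Hz.
4. Apply the same settings to the relative-power analysis in 13.3.
5. Keep the 30-60 Hz boxcar result as a sensitivity analysis, because Protocol 8.3 wants comparison with existing ketamine data. State for that analysis whether the 60 Hz bin is counted.

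The taper and the lower upper edge are both needed, since neither alone deals with both leakage and mains.

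The cost is a text change and reprocessing, with no new data. Activity at 55-60 Hz drops out of the main gamma measure. The taper gives up some effective data, which the overlap largely recovers. It must be applied before or within the LORETA step; the documents do not describe that software's taper options, so this should be confirmed first.

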## 12.11 BLOOD AND CSF DRAWS FOR CLINICAL LABORATORY AND PHARMACOKINETIC TESTING

Blood and CSF draws for serial PK and clinical laboratory testing will be collected at defined timepoints within the SAD, MAD and CSF Capture parts according to the schedule of assessments and procedures (Tables 1, 2 and 3, respectively) and as described in section 8.6.

Blood will be stored and shipped to a LabCorp (Covance) central laboratory who will perform PK analysis of (2R,6R)-Hydroxynorketamine using a LC/MS/MS method to capture the following parameters: Cmax, tmax, Cmin, AUC0-∞, AUC0-Tau, CL, Vz, CLR, t1/2. CSF samples will be analyzed at NIH using an alternate LC/MS/MS method assessing total (2R,6R)-Hydroxynorketamine concentrations at 3 collection timepoints (predose, 1-hr postdose and 8-hr postdose).

Subjects must have consented to participate before the screening blood draw. Blood draws collected for PK *and* clinical laboratory testing will be comprised of a total of approximately 16 mL from each Subject. Blood draws collected *only* for clinical laboratory testing will be comprised of a total of approximately 11 mL from each Subject. Blood draws collected for *only* PK testing will be comprised of a total of approximately 5 mL from each Subject. The maximum amount of blood draw (cumulatively) for any Subject will be approximately 219 mL.

Blood draws collected for clinical laboratory testing will include 4.5 mL for chemistry panel, 4 mL for hematology panel, 2.7 mL for coagulation panel, and 8.5 mL for serology

panel (see Table 9-11). Blood draws collected for PK will include approximately 5 mL for primary and repeat analysis of the drug substance [(2R,6R)-Hydroxynorketamine] and remaining samples will be stored.

CSF draws will be comprised of a total of approximately 10 mL from each subject and will consist of 3.5 mL for both metabolomics and proteomics and 3 mL for PK (Table 12). Subjects will have a spinal catheter placed for sample collection. Spinal catheter placement, sample collection and storage details will be provided in the MOP.

Sample	Total Volume (mL)	Clin. Lab. Volume	PK Volume (mL)
		(mL)	
Screening Draw	20	20	NA
Day -1 Draw	11	11	NA
Day 1 Draw	16	11	5
(preinfusion)			
Day 1 Draw (end-of-	5	NA	5
infusion)			
Day 1 Draw (1-hour	5	NA	5
after the start of the			
infusion)			
Day 1 Draw (2-hour	5	NA	5
after the start of the			
infusion)			
Day 1 Draw (4-hour	5	NA	5
after the start of the			
infusion)			
Day 1 Draw (8-hour	5	NA	5
after the start of the			
infusion)			
Day 1 Draw (12-hour	5	NA	5
after the start of the			
infusion)			
Day 2 Draw (24-hour	16	11	5
after the start of the			
infusion)			
Day 3 Draw (48-hour	16	11	5
after the start of the			
infusion)			
Total Blood Draw	109		

Table 9: Blood draw volumes and uses for SAD study

## Table 10: Blood draw volumes and uses for MAD study

Sample	Total Volume (mL)	Clin. Lab. Volume (mL)	PK Volume (mL)
Screening Draw	20	20	NA
Day -1 Draw	11	11	NA
Days 1, 4, 8, 11 Draw	64 (4 × 16)	44 (4 × 11)	20 (4 × 5)
(preinfusion)			

Days 1, 4, 8, 11 Draw	20 (4 × 5)	NA	20 (4 × 5)
(end-of-infusion)			
Days 1, 11 Draw	$10(2 \times 5)$	NA	10 (2 × 5)
(1 hour after the start of			
the infusion)			
Days 1, 11 Draw	10 (2 × 5)	NA	10 (2 × 5)
(2 hours after the start of			
the infusion)			
Days 1, 11 Draw	$10(2 \times 5)$	NA	$10(2 \times 5)$
(4 hours after the start of			
the infusion)			
Days 1, 11 Draw	$10(2 \times 5)$	NA	$10(2 \times 5)$
(8 hours after the start of			
the infusion)			
Days 1, 11 Draw	$10(2 \times 5)$	NA	$10(2 \times 5)$
(12 hours after the start			
of the infusion)			
Days 2, 11 Draw	32 (2 x 16)	22 (2 x 11)	10 (2 x 5)
(24 hours after the start			
of the infusion)			
Total Blood Draw	197		

### Table 11: Blood draw volumes and uses for CSF Capture study

Sample	Total Volume (mL)	Clin. Lab. Volume	PK Volume (mL)
_		(mL)	
Screening Draw	20	20	NA
Day -1 Draw	11	11	NA
Day 1 Draw	16	11	5
(preinfusion)			
Day 1 Draw (end-of-	5	NA	5
infusion)			
Day 1 Draw (1-hour	5	NA	5
after the start of the			
infusion)			
Day 1 Draw (2-hour	5	NA	5
after the start of the			
infusion)			
Day 1 Draw (4-hour	5	NA	5
after the start of the			
infusion)			
Day 1 Draw (8-hour	5	NA	5
after the start of the			
infusion)			
Day 1 Draw (12-hour	5	NA	5
after the start of the			
infusion)			
Day 2 Draw (24-hour	16	11	5
after the start of the			
infusion)			
Total Blood Draw	93		

Sample	Total Volume (mL)	Proteomics Volume (mL)	Metabolomics Volume (mL)	PK Volume (mL)
Day 1 Draw (preinfusion)	10	3.5	3.5	3
Day 1 Draw (end-of- infusion)	10	3.5	3.5	3
Day 1 Draw (8-hour after the start of the infusion)	10	3.5	3.5	3
Total CSF Draw	30	10.5	10.5	9

Table 12: CSF draw volumes and uses for CSF Capture study

# 12.12 BLOOD AND CSF DRAW SAMPLE COLLECTION, HANDLING, SHIPPING, AND RECEIVING

Blood and CSF draws collected for clinical laboratory analysis and for PK will be collected, labeled, inventoried, stored, and shipped as described in the detailed in the MOP.

## 12.13 URINE COLLECTION, HANDLING, SHIPPING, AND RECEIVING

Urine samples collected for clinical laboratory analysis and for PK will be collected, labeled, inventoried, stored, and shipped as described in the detailed in the MOP.

# **12.14 PHARMACOKINETIC ANALYTICAL PROCEDURES**

All blood samples will be processed to plasma for analysis. Analytical procedures will conform to a predetermined bioanalytical method.

# **12.15 PHARMACOKINETIC PARAMETERS**

Blood samples will be analyzed for (2R,6R)-Hydroxynorketamine levels using an LC/MS/MS analytical method to determine plasma concentration levels in order to calculate the following PK parameters:  $C_{max}$ ,  $t_{max}$ ,  $C_{min}$ , AUC0- $\infty$ , AUC0-Tau, CL, Vz, CLR,  $t_{1/2}$ .

## 12.16 SUBJECT RELEASE, FOLLOW-UP, AND STUDY CLOSE

All Subjects will be released from study confinement according to the Time and Events Schedule for the SAD study (Table 1), MAD study (Table 2) and CSF Capture study (Table 3) following a final consultation with the PI or a designee. All Subjects are required to conform to all follow-up visits or phone calls according to the Time and Events Schedule for the SAD study (Table 1), MAD study (Table 2) and CSF Capture study (Table 3). A Subject will be considered to have completed the study if he or she completes the final blood draw collected for clinical laboratory analysis and for PK.

# **13.0 STATISTICAL ANALYSIS**

Detailed summaries of the statistical analysis plan for 1) all safety data; 2) all PK; and 3) all qEEG data will be prospectively described in a Statistical Analysis Plan section of the MOP.

# **13.1 SAFETY DATA**

All investigational product and protocol procedure related AEs will be listed, and if the frequency of events allows, safety data will be summarized using descriptive methodology.

Each incidence of investigational product and protocol procedure related AEs will be presented by severity and by association with investigational product as perceived by the PI. Symptoms/AEs reported to occur prior to study entry will be distinguished from those reported as new or increased in severity during the study. All AEs and symptoms will be classified by the most suitable term using the MedDRA and summarized by SOC and preferred term, by severity, by relationship to study drug and study procedure, and by study drug dose.

The number of investigational product-related SAEs will be reported.

Safety parameters that will be assessed include clinical lab parameters, VS, and ECG parameters. The parameters will be listed and summarized using standard descriptive statistics. Additional analysis will be performed if warranted upon review of the data.

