## **3.0 STUDY OBJECTIVES AND ENDPOINTS**

The primary objective of this study is to determine the safe dose range and tolerability of (2R,6R)-Hydroxynorketamine HCl administered via a slow IV infusion (40 minutes) to healthy volunteers. A second primary objective for this study is to assess the pharmacokinetics (PK) of (2R,6R)-Hydroxynorketamine HCl in serum following single and multiple dose administrations.

The exploratory objective of this study is to collect quantitative electroencephalography (qEEG) data as a PD biomarker (SAD). Another exploratory objective of this study is to assess the concentration of (2R,6R)-Hydroxynorketamine HCl collected from cerebrospinal fluid following administration of a single dose(CSF capture).

Study endpoints include completion of all dosing levels and timepoints with full collection of all safety data, adverse events (AEs) tabulation, clinical laboratory tests, PK endpoints (eg,  $C_{max}$ , time to  $C_{max}$  [tmax], minimum plasma concentration [ $C_{min}$ ], area under the plasma concentration-time curve from 0 to infinity [AUC0- $\infty$ ], area under the plasma concentration-time curve during the dosing interval [AUC0-Tau], systemic plasma clearance (CL), volume of distribution during terminal phase [ $V_z$ ], renal clearance [CLR], terminal half-life [t1/2]).

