#### Study Halting Rules

If any of the following events occur, the study will be stopped:

- Any subject develops an SAE through the last study visit.
- 2 or more subjects in any cohort experience a Grade 3 (severe) AE, including unsolicited clinical, ECG, VS, and laboratory AEs, that is of the same type (preferred term) and occurring in the same SOC.
- Any subject develops an episode of anaphylaxis within 24 hours after receiving the study drug.

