#### Dose Escalation Halting Rules

The PI must review the following criteria before dose escalation:

- SAD: A review of all available safety data for the cohort to Day 3 demonstrates that the study halting criteria described below have not been met.
- MAD: A review of all available safety data to Day 12, at a minimum, demonstrates that the dose-escalation halting criteria described below have not been met.

If any of the following dose escalation halting rules are met in either the SAD or MAD parts, escalation to the next planned dose cohort will not proceed until all available study data have been reviewed by the PI, the Medical Monitor and the Study Sponsor:

- Any subject develops an SAE.
- Any subject experiences a Grade 3 (severe) AE.
- 2 or more subjects in a cohort experience a Grade 2 (moderate) or greater AE that is of the same type (preferred term) and occurring in the same SOC.

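### Protocol 13.1 counts only product-related SAEs, and neither document specifies an all-cause SAE count, although any SAE halts the study

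*Protocol*

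**What the plan says.** Protocol 3.0 puts safety first: "The primary objective of this study is to determine the safe dose range and tolerability". Protocol 13.1 then sets out the safety outputs in four steps that do not share one scope.

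- Listing: "All investigational product and protocol procedure related AEs will be listed, and if the frequency of events allows, safety data will be summarized".
- Incidence: "Each incidence of investigational product and protocol procedure related AEs will be presented by severity and by association with investigational product".
- Summary: "All AEs and symptoms will be classified by the most suitable term using the MedDRA and summarized by SOC and preferred term". This sentence continues with severity, relationship to drug and to procedure, and dose. The synopsis and section 8.7 repeat it without a relatedness filter.
- SAE count: "The number of investigational product-related SAEs will be reported".

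The halting rules in Protocol 10.3 carry no attribution condition. The study rule is "Any subject develops an SAE through the last study visit", the dose-escalation rule is "Any subject develops an SAE", and the individual rule for the MAD part is also any SAE. Section 7.0 applies the 10.3 criteria to the CSF part. Section 12.9 sends every SAE to the sponsor whatever its cause and records every AE on the case report form.

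In the SAP, section 8.1 makes AE tabulation a primary outcome, section 7 includes every Safety Population subject by sub-study, cohort and pooled placebo, and section 12.5 requires listings behind all summaries. Section 12.6 defines AE, relatedness and seriousness. It names no AE or SAE table.

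**The concern.** A first-in-human safety report is expected to give the number of subjects with a serious event in each dose group, before anyone's view of causation is applied. Here the stated number depends on the PI's attribution, while the rule that stops the trial does not. The two can disagree about the same event: the study stops for an SAE, and the reported SAE number is zero.

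Procedure-related SAEs raise the same problem. The listing sentence covers events related to product or procedure, but the SAE sentence covers product only. The CSF part involves lumbar puncture with a catheter, and Protocol 4.0 itself names bleeding, infection and headache as its risks.

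**Working it through.** No alpha, power or sample-size figure is involved, so the check is to follow three kinds of SAE through the stated rules.

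| SAE judged to be | Halts the study (10.3) | In the 13.1 SAE count | In the 13.1 listing sentence | In the 13.1 all-AE summary | In a listing under SAP 12.5 |
|---|---|---|---|---|---|
| Product-related | Yes | 1 | Yes | Yes | Yes |
| Procedure-related only | Yes | 0 | Yes | Yes | Yes |
| Related to neither | Yes | 0 | No | Yes | Yes |

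**SAE count.** In the last two rows the halting rule and the reported count part company. The all-AE summary does not fill the gap. It is broken down by severity, attribution and dose, and severity (mild, moderate or severe in SAP 12.6) is not seriousness. No sentence asks for a breakdown by seriousness, so the number of SAEs cannot be read from that summary.

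**AE listing.** The third row shows an inconsistency rather than an omission. The listing sentence in 13.1 leaves unrelated events out. The all-AE summary in the same section, read with SAP 12.5, brings them back in.

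**The filter itself.** Protocol 12.9 has two categories. An event with plausible timing is related if other factors cannot reasonably explain it, or if it is a known or predicted reaction. SAP 12.6 has five grades and counts possible, probable and definite as related. Take an SAE with plausible timing and a reasonable alternative explanation, not previously known for the drug or its class. It is not related under Protocol 12.9. If the investigator grades it possible, it is related under SAP 12.6. The count is then 0 or 1 for the same event, depending on the document applied. Both definitions concern the study product, and neither document defines relatedness to a procedure.

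**Other SAP sections.** Sections 12.7 to 12.11, 12.13 and 12.14 each name their outputs, and 12.12 states that no descriptive statistics will be given. Section 12.6 alone contains definitions and no output.

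**Illustration of size.** Take a SAD or MAD dose group with 6 active subjects and one SAE judged unrelated, with exact (Clopper-Pearson) two-sided 95% limits:

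- Filtered count, 0/6: upper limit = 1 − 0.025^(1/6) = 0.459, or 46%.
- All-cause count, 1/6 = 17%: lower limit = 1 − 0.975^(1/6) = 0.004, or 0.4%. The upper limit solves (1 − p)^6 + 6p(1 − p)^5 = 0.025, giving p = 0.641, or 64%.

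Neither document plans a per-cohort SAE proportion or interval, so these figures only show what one event means in a group of six.

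**The case against.** The strongest reply is that 13.1 promises a count of product-related SAEs without saying that other SAEs go unreported. An SAE is an AE, so it falls within the all-AE summary and its supporting listing. It also goes to the sponsor regardless of cause, and Protocol 10.3 requires decisions on all halts to be documented and sent to the IRB. Halting rules and a related-SAE count serve different purposes, so a difference between them need not be a contradiction.

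Most of this stands, and it rules out three stronger readings that a reader might infer:

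- **That severity is shown for related AEs only.** The incidence sentence alone suggests it, but the all-AE summary in the same section includes severity, relationship and dose.
- **That unrelated events are hidden.** They appear in the all-AE summary and, through SAP 12.5, in a listing. An SAE that stops the study cannot pass unnoticed.
- **That the comparison with placebo is broken.** SAP section 7 keeps every Safety Population subject, by cohort and pooled placebo, with no relatedness filter.

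The reply does not supply the missing output. Safety oversight during the trial and a reported count at its end are different things, and only a filtered count is specified. The history of revisions records that version 2.0 took relatedness out of the stopping rules. That suggests the sponsor chose not to rely on attribution there, and the SAE count still does.

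**Conclusion.** The point holds for the SAE count. The only SAE number specified is limited to product-related events, and no all-cause count is named in either document. Each SAE judged unrelated, or related only to a procedure, lowers the reported number by one while still meeting the study halting rule. The number can also shift with the choice between two definitions of relatedness.

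For AEs the finding is narrower: the listing sentence in 13.1 conflicts with the all-AE summary beside it and with SAP 12.5. That is a matter of wording.

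This rests on reading the SAE sentence in 13.1 as the complete specification, which is reasonable because SAP 12.6 adds no table. The practical effect depends on whether any SAE occurs and how it is attributed, which the documents cannot tell us. It should be corrected before the database is locked. It does not undermine the design or the AE reporting as a whole.

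**What to change.** Amend Protocol 13.1 and add the same text to SAP 12.6:

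> Every AE is to be listed. The number of SAEs and the number of subjects with at least one SAE are to be reported regardless of relationship, by dose group and pooled placebo within each sub-study (SAD, MAD, CSF). Product-related and procedure-related events are to be shown as subsets.

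Two further details belong with it.

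- Adopt one definition of relatedness in both documents, and extend it to study procedures.
- State the time window. All AEs are monitored from dosing to the end of the study, so the all-cause count can run to the last study visit. For the month after the last dose, Protocol 12.9 specifically asks for new SAEs judged related to the product, so any SAE arising after the last visit is best shown separately.

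The cost is a few sentences and one extra table. No new data are needed, because all AEs are already recorded on the case report form. No halting rule or other clinical rule changes.
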